# Study Protocol with Statistical Analysis Plan

## Scientific Background

Loss of the interdental papilla is a frequent aesthetic concern, particularly in the anterior region where even minor deficiencies create visible black triangles. These deficiencies contribute to plaque accumulation, food impaction, and phonetic disturbances, in addition to compromising smile harmony. Earlier attempts to reconstruct missing papillae through surgery often yielded unpredictable outcomes, largely due to the delicate blood supply of the papillary region. As a result, attention has shifted toward non-surgical injectable biomaterials designed to restore soft-tissue volume with minimal invasiveness.

Hyaluronic acid (HA) dermal fillers have become widely used in aesthetic and periodontal therapy due to their biocompatibility, hydrophilicity, and ability to stimulate wound healing. Clinical studies have consistently reported partial or complete closure of black triangles following repeated HA injections. Injectable platelet-rich fibrin (i-PRF), prepared via low-speed centrifugation, represents an autologous alternative that provides a fibrin scaffold enriched in platelets and leukocytes. Its gradual release of growth factors promotes angiogenesis, fibroblast proliferation, and extracellular matrix formation.

Despite increasing interest, direct comparisons between these two materials are scarce, and previous trials have not used a split-mouth design to minimize interpatient variability. This study directly compares HA and i-PRF administered under identical intraoral conditions. We hypothesized that both would yield significant improvement in papilla fill without clinically meaningful differences between them.

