## Study design

This randomized split-mouth clinical trial included 13 systemically healthy adults with a total of 65 papilla deficiencies in the aesthetic zone. The study was approved by the Altınbaş University Ethics Committee. All participants provided written informed consent.

Inclusion criteria required  $\geq 2$  papillae classified as Papilla Presence Index (PPI) class 2 or 3, probing depths  $\leq 3$  mm, and plaque and bleeding scores below 15%. Exclusion criteria included PPI class 4, diastema, active periodontal disease, smoking, pregnancy, systemic conditions influencing healing, anticoagulant use, and previous surgical papilla reconstruction.

For each participant, one side was randomly assigned HA and the contralateral side i-PRF. The clinical examiner underwent intra-examiner calibration until repeated measurements were consistent within  $\pm 1$  mm. Outcome assessments were performed by a blinded examiner.

For i-PRF sites, 10–20 mL of venous blood was collected into plastic tubes and centrifuged at 700 rpm for 3 minutes. The upper orange plasma layer was aspirated and transferred to 1-mL insulin syringes. Injections were delivered within 5 minutes to ensure liquid consistency before polymerization.

All treatments were performed with buccal infiltration anesthesia. HA or i-PRF (0.1–0.2 mL) was injected from the buccal aspect, 2–3 mm apical to the papilla tip, at a 45° angle. A single

puncture per session was used to minimize trauma. Slight blanching indicated correct placement. Each papilla received three injections at baseline, week 3, and week 6.

Participants avoided mechanical oral hygiene for 24 hours and interdental brushes for one week, replacing them with 0.12% chlorhexidine rinses. Modified Bass brushing resumed the following day.

Standardized photographs were obtained using a custom photograph standardization device (PSD), enabling consistent image acquisition. Black triangle height (BTH), width (BTW), area (BTA), and papilla height (PH) were measured at baseline, 1 month, and 3 months using ImageJ. PPI was recorded visually. Radiographs were taken to measure the distance between the interdental bone crest and contact point (IBC-ICP). Keratinized tissue thickness (KTT) was measured at baseline.

Pain was assessed after each injection using a VAS scale from 0 (none) to 10 (worst). Aesthetic satisfaction was rated at each visit using a VAS scale from 0 (not satisfied) to 10 (highly satisfied).

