## Statistical Analysis Plan

The data were analysed using the Statistical Package for the Social Sciences (SPSS) version 26.0. The normality of distribution for the numerical variables related to the patients and the evaluated interdental papilla sites was assessed based on skewness and kurtosis values. Normality of continuous data will be assessed using the Shapiro–Wilk test and visual inspection of Q–Q plots. A reference range of  $\pm 1.96$  was adopted as the criterion for normal distribution (Kalayci, 2005).

For each material, changes over time from baseline to follow-up will be analysed using repeated-measures ANOVA when assumptions are met, or the Friedman test in the case of non-parametric or ordinal data. Post-hoc pairwise comparisons between time points will include Bonferroni adjustments. Since the study design is split-mouth, inter-group comparisons between HA and i-PRF at each time point, as well as comparisons of change scores, will use paired t-tests for normally distributed variables and Wilcoxon signed-rank tests otherwise. PPI, being ordinal, will be evaluated with non-parametric paired procedures. Subgroup analyses will be performed separately for maxillary and mandibular papillae using similar paired or repeated-measures methods. Patient-reported VAS outcomes will be analysed using repeated-measures methods for within-group changes and paired testing for between-group differences.

Comparisons of KTT and IBC-ICP measurements across jaw localizations and treatment groups, as well as intergroup analyses of clinical outcome variables, were performed using the One-Way ANOVA test. Intragroup comparisons of variables measured at different time points were conducted using the Repeated Measures ANOVA. Where applicable, Post Hoc tests were employed to further investigate significant intergroup differences.

Additionally, to evaluate the relationship between KTT and IBC-ICP measurements and the percentage changes in clinical parameters, the Spearman correlation test was used. In interpreting the correlation coefficients, a range of 0.00–0.30 was considered low, 0.30–0.70 moderate, and 0.70–1.00 high. A significance level of  $p < 0.05$  and  $p < 0.01$  was adopted for all statistical analyses.

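### The plan cannot test its hypothesis of no clinically meaningful HA versus i-PRF difference in papilla fill: every between-material test is against zero, with no margin, confidence interval or reading rule

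*Combined protocol and SAP*

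**What the plan says.** The documents state one hypothesis, at the end of the Scientific Background: "We hypothesized that both would yield significant improvement in papilla fill without clinically meaningful differences between them". It has two parts: improvement with each material, and no difference of clinical importance between the materials. Both concern papilla fill.

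For the between-material part, the Statistical Analysis Plan provides these tests:

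- **Continuous outcomes, at each time point and as change:** "comparisons of change scores, will use paired t-tests for normally distributed variables and Wilcoxon signed-rank tests otherwise".
- **Papilla Presence Index:** "PPI, being ordinal, will be evaluated with non-parametric paired procedures".
- **A second description of the between-group analysis, in the third paragraph:** "intergroup analyses of clinical outcome variables, were performed using the One-Way ANOVA test".

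The only decision thresholds are p-values of 0.05 and 0.01. Both are named in a sentence saying that the level "was adopted for all statistical analyses", and neither is identified as the one that decides.

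Patient-reported VAS scores are also compared between materials by paired testing. Pain and satisfaction are not papilla fill, so those tests are outside this point.

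**The concern.** Whether a difference is clinically meaningful is a question of size. A test against zero asks only whether the data are compatible with no difference at all. It needs a margin, or at least an interval estimate, before it can say anything about clinical importance.

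If the plan is followed exactly, the between-material part of its only hypothesis stays unanswered whatever the p-values are. The trial could find a non-significant difference while a sizeable one remains plausible, or a significant difference too small to matter. Nothing in the plan stops a report from drawing the wrong conclusion in either case.

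**Working it through.** **1. Search for a size criterion.** Three figures in the documents might be mistaken for one:

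| Figure | Section | Purpose |
|---|---|---|
| ±1 mm | Study design | examiner repeatability |
| ±1.96 | Statistical Analysis Plan | normality range |
| 0.30 and 0.70 cut-offs | Statistical Analysis Plan | reading correlation coefficients |

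None is a treatment-difference margin. No equivalence test, minimal important difference or confidence interval appears anywhere.

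**2. Null hypothesis of each test.** The paired t-test, the Wilcoxon signed-rank test, paired non-parametric procedures and one-way ANOVA all take no difference as the null unless another value is specified. None is specified.

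**3. Inputs for an illustration.** The plan has no power or precision figure to reproduce. From Study design: 13 participants, 65 papillae, one side per material. Assumed: a two-sided 5% test, and results in SDs of the paired difference at the unit analysed, because no SD is given. The plan does not fix the unit, so two are shown:

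- *Participant level:* n = 13 pairs, assuming every participant has a treated papilla on each side. The entry criterion of at least two papillae does not guarantee this.
- *Site level:* 65 / 2 = 32.5, so at most 32 pairs, treated as independent. This ignores clustering within participants and is optimistic. A site-level SD is also not a participant-level SD, so the columns below are not on one scale.

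**4. Formulas.** Half-width of the 95% interval = t(0.975, n − 1) / √n. Probability of missing a true difference d = P(|T| < t(0.975, n − 1)), where T is noncentral t with n − 1 degrees of freedom and noncentrality d√n.

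| | 13 participant pairs | 32 site pairs |
|---|---|---|
| Critical t | 2.179 | 2.040 |
| Half-width (SD) | 2.179 / √13 = 0.60 | 2.040 / √32 = 0.36 |
| Missed, d = 0.5 | 62% | 22% |
| Missed, d = 0.8 | 25% | 0.8% |

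If 0.01 were the deciding level, the 13-pair miss rates would be 84% and 53%. The plan does not say that it is.

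**5. Both directions, 13 pairs.** The observed difference is t / √13.

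- p = 0.20: t = 1.356, difference 0.376 SD, 95% interval 0.376 ± 0.604 = −0.23 to 0.98 SD.
- p = 0.03: t = 2.461, difference 0.682 SD, 95% interval 0.682 ± 0.604 = 0.08 to 1.29 SD.

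The two intervals overlap over most of their length. Without a margin, neither p-value says whether the difference matters.

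**6. What an equivalence claim would need.** Two one-sided tests, true difference zero, power by integration over the sample SD:

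| | One-sided 5% (90% interval) | One-sided 2.5% (95% interval) |
|---|---|---|
| Margin for 80% power, 13 pairs | 0.86 SD | 0.98 SD |
| Power at an assumed 0.5 SD margin, 13 pairs | 13% | 4% |
| Pairs for 80% power at that margin | 36 | 44 |

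**The case against.** The strongest reply is that the sentence is a background expectation, not a registered equivalence objective. Just before it, the documents describe the study as a direct comparison of the two materials, and difference tests suit a comparison. That is fair as far as it goes. But this is the only hypothesis stated, and the plan offers no other means of judging it.

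A reader might infer that the investigators intend to treat a non-significant result as proof of similarity. The documents do not support that: no section says so, and none calls the trial an equivalence or non-inferiority trial. The defect is an unanswered question left open to misreading, not a wrong decision rule.

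A reader might also extend the point to VAS pain and satisfaction, since the plan applies "paired testing" there too. The hypothesis is about papilla fill, so it does not reach them.

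Finally, 65 papillae carry more information than 13 pairs if sites are the unit. This stands as a reason to show both units. It does not remove the problem: even on the optimistic site-level assumption there is an interval of ±0.36 SD and no margin to judge it by.

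**Conclusion.** The concern holds for the between-material part of the hypothesis and the papilla-fill outcomes. The planned tests can settle that part in neither direction. The within-material part is addressed by the repeated-measures or Friedman analyses and is unaffected.

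The logical gap needs no assumption. The figures that show its size do: a two-sided 5% test, complete pairs, and effects in SD units. They cannot be translated into clinical importance, because the documents give neither an SD nor a margin, so no interval above should be called large or small in clinical terms.

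This should be fixed before the between-material result is interpreted. The data remain usable.

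**What to change.** 1. **Estimates and intervals.** In the Statistical Analysis Plan, report the HA minus i-PRF paired difference in change from baseline to 3 months, with its 95% confidence interval, for black triangle height, width and area and for papilla height. Use one mean per side per participant, or a model with participant as the cluster. Where Wilcoxon is used, give the Hodges-Lehmann estimate with its signed-rank interval. With 13 untied pairs the limits are the 18th and 74th of the 91 ordered Walsh averages: 2 × P(W ≤ 17) = 0.048, so coverage is 95.2%.
2. **Papilla Presence Index.** Summarise each side by a measure suited to ordinal data, such as the median class change or the proportion of papillae that improved. Tabulate how many participants did better on HA, equally, or better on i-PRF.
3. **Reading rule.** Add: *A non-significant p-value is not evidence of equivalence, and a significant p-value alone is not evidence of a clinically meaningful difference.*
4. **Aim.** State the between-material aim as estimation, in a dated and disclosed change that leaves the present hypothesis visible. The plan is partly in the past tense ("The data were analysed using the Statistical Package for the Social Sciences (SPSS) version 26.0"), so if data had already been seen, label this change and the choice of 3 months post hoc.
5. **Equivalence claims.** Claim no clinically meaningful difference only if a justified margin for one named outcome and time point was fixed before data were seen and the interval lies wholly inside it. State the confidence level: 90% for two one-sided 5% tests, 95% for 2.5%. A margin set later supports exploratory statements only.

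**Cost.** Revised wording and intervals from data already collected; no extra patients. The permitted conclusion is less favourable. Estimation alone will not confirm the hypothesis, and with 13 pairs an equivalence claim would probably be inconclusive unless the margin were wide.

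### With no untreated or sham site, the before-after tests show change from baseline on each side but cannot show that either material caused it

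*Combined protocol and SAP*

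**What the plan says.** The Scientific Background sets the aim as a head-to-head comparison: "This study directly compares HA and i-PRF administered under identical intraoral conditions". The hypothesis has two halves: "We hypothesized that both would yield significant improvement in papilla fill without clinically meaningful differences between them". The verb in the first half credits the improvement to the materials.

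Under Study design, "For each participant, one side was randomly assigned HA and the contralateral side i-PRF". Every study papilla receives one of the two active materials. No untreated, sham or saline site, run-in period or natural-history benchmark is described.

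The SAP tests the first half of the hypothesis one material at a time: "For each material, changes over time from baseline to follow-up will be analysed using repeated-measures ANOVA when assumptions are met", or by the Friedman test, with Bonferroni-adjusted comparisons between time points. The second half is tested by paired t-tests or Wilcoxon signed-rank tests, including on change scores.

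**The concern.** Randomisation and the blinded examiner protect the contrast between HA and i-PRF. They do not protect the contrast between baseline and follow-up, and the first half of the hypothesis rests on that contrast alone.

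Study design describes several influences that reach both sides of the mouth:

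- the same anaesthesia, needle route and injected volume range, at three sessions;
- chlorhexidine rinses and a change in cleaning: "Participants avoided mechanical oral hygiene for 24 hours and interdental brushes for one week". That this was repeated after each session is an inference; the text does not say so;
- entry on baseline status ("papillae classified as Papilla Presence Index (PPI) class 2 or 3"), which allows regression to the mean.

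If such influences improve the measurements on both sides, both before-after tests can be significant and the paired test non-significant with no contribution from either material. The planned analysis could then confirm the hypothesis even if neither material has an effect. At stake is a published statement that both materials are effective, which this design cannot support.

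**Working it through.** The documents give no sample-size calculation, effect size, SD or margin, so there is no figure of the plan's own to reproduce. The check has two parts.

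**1. What each comparison estimates.** Write the mean change on each side as

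- HA side: a + s
- i-PRF side: b + s

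where a and b are the material effects and s is whatever both sides share. The before-after tests address a + s and b + s. The paired test addresses (a + s) − (b + s) = a − b. Two observed means cannot determine three unknowns: the data give a − b but neither a nor b. A result of a − b = 0 fits a = b = 0 as well as it fits two equally effective materials.

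**2. How often the hypothesised pattern arises when a = b = 0.**

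Inputs from the documents:

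- 13 participants (Study design: "This randomized split-mouth clinical trial included 13 systemically healthy adults with a total of 65 papilla deficiencies in the aesthetic zone").
- Three time points, giving three pairwise comparisons, so Bonferroni gives 0.05/3 for the within-material tests.
- Paired t-test between sides at 0.05. The SAP also mentions one-way ANOVA for between-group analyses; I used the paired test because it fits the split-mouth design.

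Assumptions, because the documents are silent: two-sided tests; one normally distributed change score per side per participant; between-side correlation 0.5–0.7; shared shift d in SD units of the change score.

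The pattern counts as present when both one-sample t-tests show improvement and the paired t-test has p > 0.05. With 12 degrees of freedom the critical t is 2.179 at 0.05 and 2.779 at 0.05/3. A side is therefore significant when its observed mean change exceeds 2.179/√13 = 0.60 observed SDs, or 2.779/√13 = 0.77 observed SDs. That is why the pattern becomes common only at large shifts. Its frequency cannot exceed 95%, because the paired test rejects in 5% of trials when a = b.

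| Shared shift d (SD) | Within-tests at 0.05 | Within-tests at 0.05/3 |
|---|---|---|
| 0 | under 1% | under 1% |
| 0.25 | 4–6% | 1–2% |
| 0.5 | 21–25% | 8–11% |
| 0.75 | 53–56% | 31–34% |
| 0.8 | 60–63% | 37–41% |
| 1.0 | 81–82% | 63–65% |

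The ranges run over correlation 0.5 to 0.7. At correlation 0 the 0.05 figures are lower at 0.5 SD (15%) and about the same at 1.0 SD (80%).

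**How large might s be?** The documents do not say. As an illustration for regression to the mean alone, suppose one-sided selection of the worst 20–50% of sites and measurement reliability r of 0.6–0.9, all assumed. The expected change is (1 − r) × m, where m is the mean baseline of the selected sites in SD units:

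- r = 0.9, worst 50%: 0.1 × 0.80 = 0.08 baseline SD, or 0.18 SD of the change score.
- r = 0.6, worst 20%: 0.4 × 1.40 = 0.56 baseline SD, or 0.68 SD of the change score.

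So d would be about 0.2–0.7. On its own that would usually not make the pattern the likely result; other shared influences would have to add to it.

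**The case against.** The strongest reply is that the pattern needs a large shared shift and nothing in the documents shows one. Entry requires plaque and bleeding scores below 15%, probing depths of at most 3 mm and no active periodontal disease, which limits the room for a hygiene effect. If 3 months is counted from baseline, a one-week brush restriction after the week-6 injection would be over by then. Standardised photographs, ImageJ measurement and a blinded examiner limit drift. PPI class 4 is excluded, so even the direction of regression to the mean is uncertain. The stated purpose is the head-to-head comparison, which the paired test of change scores already serves, and the Background cites consistent earlier HA results.

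Much of this stands, and it rules out several stronger readings:

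- A reader might infer that improvement on both sides without a difference is what to expect if neither material works. With inert materials and no shared change it occurs in under 1% of trials.
- A reader might infer that the analysis would confirm the hypothesis whatever the truth. It could do so without a material effect, but how often depends on a shift the documents do not quantify.
- A reader might infer that the within-material tests are uninformative. They do support a descriptive statement that papilla measurements changed from baseline.
- A reader might count supervised brushing among the shared influences. The text says only that modified Bass brushing resumed.

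The reply does not remove the identification problem. A small shared change is plausible, but the design cannot demonstrate it. The cited HA studies are not said to have been controlled, and for i-PRF the Background gives a mechanism and no clinical result. If 1 month is counted from baseline (the origin is not stated), that assessment falls about one week after the week-3 injection, when transient swelling or injected volume could still act on both sides.

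**Conclusion.** The concern holds as a limit on attribution. The within-material tests can show change from baseline; they cannot show that HA or i-PRF caused it, and a null difference between sides adds no evidence that either works. This follows from the allocation and needs no numerical assumption.

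The practical risk does depend on assumptions. With 13 participants, zero material effect and correlation 0.5–0.7, a false confirmation is more likely than not once the shared shift reaches about 0.75 SD with within-material tests at 0.05, or about 1 SD with the Bonferroni adjustment. It is uncommon at 0.25 SD or below. The absence of a margin for a clinically meaningful difference is a separate matter and is not counted here.

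**What to change.** No extra arm, participants or data are needed. Change the wording of the hypothesis and add a conclusion rule to the SAP:

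1. Report within-material results as uncontrolled change from baseline under treatment plus aftercare, as estimates with 95% CIs, and not as evidence of efficacy.
2. Base the trial's inferential conclusion on the randomised HA minus i-PRF difference in change, with its 95% CI.
3. State that similarity between sides does not show that either material works.

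The cost is a narrower claim: the trial could report how the two materials compare and how papillae changed under treatment, but not that both are effective.
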